##### BI 1569912 Specific Risk Minimization Measures:

- In each dose group, the three cohorts (see above) will be separated by at least 48 hours (between first subjects of each cohort) which is expected to cover the period of highest risk/ peak effect.
- Interim measurements of BI 1569912 plasma levels will be performed. The expected geometric mean systemic exposure ( $C_{\max}$ ,  $AUC_{0-24h}$ ) in the next higher dose group will be estimated based on current and preceding doses using a dose proportionality or model-based approach, as applicable. The next higher dose level will only be administered, if the predicted geometric mean values of  $C_{\max}$  or  $AUC_{0-24h}$  do not exceed the defined exposure limits of 1560 nM for  $C_{\max}$  or 2490 nM\*h for  $AUC_{0-24h}$ .

(see Section [1.3.2.1](#)) or, if no individually observed value of the current dose group exceeds the defined exposure limits of 1560 nM for  $C_{\max}$  or 2490 nM\*h for  $AUC_{0-24h}$ .

- 
- In the BA/ FE-Part, only one dose strength will be tested, either the 5 mg or 2.5 mg or 0.5 mg tablet. Only the highest dose strength, as demonstrated in the SRD-Part to be safe and tolerable, will be tested, reduced by a safety factor of at least 2. Before starting the BA/ FE-Part, a summary of safety and tolerability data (including AEs, SAEs, ARs and SARs) generated so far during the course of the trial will be submitted via substantial amendment.
  - Subjects will be confined to the study site under close observation for at least 72 hours after drug administration at the trial site and will be discharged only after a formal assessment and confirmation of fitness by an investigator or qualified designee. During in-house confinement, subjects will be under medical observation and thoroughly monitored for both, expected and unexpected adverse events.
  - Subjects will be evaluated with electrophysiological and functional assessments to identify any possible adverse event. Specifically, any signs of pro-convulsive activity of the brain will be assessed by repeated EEG measurements in each dose group. Close neurological/ psychiatric evaluation using a standardized clinical assessments for the detection of neurological symptoms, the Columbia-Suicide Severity Rating Scale for the assessment of suicidality and the CADSS for the assessment of suspected dissociative symptoms. The occurrence of anticipated dissociative symptoms will be reduced by quiet ambient conditions during and after drug administration.
  - The preliminary determination of the REP is up to 36 hours.

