#### 1.3.2.1 Maximum systemic exposure and safety margins

In the 6-week oral toxicity GLP dog study, the dose of 1 mg/ kg was free of behavioural signs and was defined as NOAEL at a mean  $C_{\text{max}}$  of 1560 nM and a mean  $\text{AUC}_{0-24\text{h}}$  of 2490 nM\*h. In the same toxicity study, the dose of 3 mg/ kg induced behavioural signs but was free of focal seizures/ convulsions at a mean  $C_{\text{max}}$  of 4490 nM and a mean  $\text{AUC}_{0-24\text{h}}$  of 7850 nM\*h. These observed behavioural signs could (at least in part) indicate exaggerated pharmacology of BI 1569912. In the dose range finding non-GLP dog study, the dose of 5 mg/ kg induced generalised convulsions at a mean  $C_{\text{max}}$  of 8230 nM and a mean  $\text{AUC}_{0-24\text{h}}$  of 14600 nM\*h.

Therefore, the maximal acceptable systemic exposure is defined as gMean  $C_{\text{max}}$  of 1560 nM and a gMean  $\text{AUC}_{0-24\text{h}}$  of 2490 nM\*h which should not be surpassed with the highest applied

dose in the SRD-Part of the study. This would be about 5-fold ( $C_{\max}$ ) and 6-fold ( $AUC_{0-24h}$ ) lower than the exposures in dog at doses inducing generalised convulsions, and about 3-fold ( $C_{\max}$  and  $AUC_{0-24h}$ ) lower than the exposures in dog at doses inducing behavioural signs.

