### Drug-related risks and safety measures

Factors of risk may derive from particular knowledge or the lack thereof, regarding (1) the mode of action, (2) the nature of the target, (3) the relevance of animal models and/ or (4) findings in non-clinical safety studies. Further aspects will be (5) risks resulting from trial medication auxiliaries, and (6) drug induced liver injury, resulting in (7) measures of risk minimization (including safety precautions and stopping rules – see Section [1.4.7](#)).

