#### Stopping Rules Related to Dose Groups:

- In case of any safety concerns, as listed below but not limited to them, the trial will be mandatorily discontinued. Occurrence of severe non-serious adverse events

considered as drug-related by the investigator in 2 subjects of the same dose group (8 subjects) in the SRD-Part, or 3 subjects of the BA/ FE group (12 subjects), or occurrence of at least one drug-related serious adverse event (SAE). Moreover, dose escalation in the SRD-Part will be terminated, if more than 3 of the actively dosed subjects at one dose level show drug-related and clinically relevant adverse events of at least moderate intensity.

- Clinical apparent seizures/ convulsions in one or more subjects in the same dose group.
- EEG changes consistent with pro-convulsive activities (e.g., spike and wave) that is considered to be drug-related in two or more subjects of the same dose group.
- Clinically relevant changes in the neurological assessment indicating dose-limiting intolerance that is considered to be drug-related in one or more subjects of the same dose group.
- Dose escalation in the SRD-Part or treatment in the BA/ FE-Part will be stopped, if at least 2 subjects on active treatment at one dose level (SRD-Part) or 2 subjects in the BA/ FE-Part have relevant individual QT prolongations, i.e., a QTc increase of greater than 60 ms from baseline and/ or an absolute QT or QTc greater than 500 ms, as confirmed by a repeat ECG recording.
- Dose escalation in the SRD-Part will be stopped, if the  $C_{\max}$  or  $AUC_{0-24h}$  of at least 1 subject of one dose group increases above the following exposure thresholds or if the estimated geometric mean exposure is expected to exceed a  $C_{\max}$  of 1560 nM or an  $AUC_{0-24h}$  of 2490 nM\*h. In this case, one or two additional dose levels lower than the planned next dose level may be given, as long as the expected geometric mean exposure values of the interim dose do not exceed these exposure thresholds. Estimation will be done based on preliminary pharmacokinetic results of preceding dose groups (see Section [7.4](#))

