The groups will be dosed consecutively in ascending order, and a time interval of at least 7 days will be maintained between the last drug administration to subjects in the previous dose group and the first drug administration to subjects in the subsequent dose group. The decision to treat the next dose group will be based upon safety, tolerability and pharmacokinetic data of all the preceding dose groups. The next dose group will only be applied, if, in the opinion of the Principal Investigator (or an authorised deputy) and the Clinical Trial Leader (or an authorised deputy), no safety concerns have arisen in the preceding dose groups (i.e., no dose-limiting events occurred) and, if none of the pre-specified trial-specific stopping criteria have been met (refer to Section [3.3.4.2](#)).

A documented safety review must take place prior to each dose escalation. Furthermore, an unscheduled safety review meeting can be requested anytime by the Principal Investigator (or an authorised deputy) or the sponsor of the study (for instance, due to the occurrence of any unforeseen adverse events).

Although no formal safety review meeting will take place within a given dose group, safety will be continuously monitored during this trial, and an individual will only be dosed in the absence of any safety concern (i.e., no dose-limiting events occurred) and if none of the pre-specified trial-specific stopping criteria have been met (refer to Section [3.3.4.2](#)).

At a minimum, the following data need to be available for review to escalate to a higher dose.

- AEs in the current and preceding dose groups up to at least 48 h post dosing, including clinically relevant findings from ancillary safety testing listed below (Note: AEs may be ongoing at the time of Safety Reviews and AE information may be subject to change prior to Database Lock)
- Results from 12-lead ECG and continuous ECG monitoring in the current and preceding dose groups up to at least 48 h post dosing
- Vital signs in the current and preceding dose groups up to at least 48 h post dosing
- Clinical laboratory tests in the current and preceding dose groups up to at least 24 h post dosing
- EEG reports up to at least 24 h post dosing
- Preliminary pharmacokinetic data of at least 3 subjects on active treatment for up to at least 24 h post dosing as per Section [7.4](#)
- Check of criteria for stopping subject treatment as per Section [3.3.4.1](#)

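### The exposure condition for the next dose in Protocol Section 1.4.7 joins its two criteria with *or*, so it is looser than the stopping rule in the same section, and Section 3.1 cites the wrong section for the stopping criteria

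*Protocol*

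**What the plan says.** Four places in the protocol bear on this.

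- **Section 1.4.7, BI 1569912 Specific Risk Minimization Measures.** "The next higher dose level will only be administered, if the predicted geometric mean values of" the two parameters stay within 1560 nM (Cmax) and 2490 nM*h (AUC0-24h); call this A. The alternative criterion follows: "or, if no individually observed value of the current dose group exceeds the defined exposure limits of 1560 nM for" the first parameter, with the AUC limit repeated; call this B.
- **Section 1.4.7, Stopping Rules Related to Dose Groups.** Escalation in the SRD part stops on either of two triggers, an individual value or a predicted mean: "at least 1 subject of one dose group increases above the following exposure thresholds or if the estimated geometric mean exposure is expected to exceed" the same limits. After such a stop, "one or two additional dose levels lower than the planned next dose level may be given", provided their expected geometric means stay within the limits.
- **Section 1.3.2.1.** The two limits are maximum acceptable geometric mean exposures "which should not be surpassed with the highest applied" dose in the SRD part. Section 1.3.2.2 likewise lets doses rise only until the maximum exposure is reached.
- **Section 3.1, SRD-Part.** The next group is dosed only "if none of the pre-specified trial-specific stopping criteria have been met (refer to Section" 3.3.4.2. The same reference appears again for dosing individuals within a group. Section 3.3.4.2 is titled Withdrawal of consent to trial participation and contains no stopping criteria.

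**The concern.** The first bullet turns the interim pharmacokinetics into a go or no-go condition for the next dose of a compound that caused convulsions in dogs. Joined by *or*, A and B are alternatives. If no one in the current group is over the limit, the condition is satisfied whatever the predicted mean for the next dose, and the cap of Section 1.3.2.1 does not bind there. Protection then comes only from the separate stopping rule. Section 3.1, which requires that rule to be checked before dosing, points the reader to a section on consent.

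A smaller drafting point: A is worded with *or* between Cmax and AUC0-24h, where Section 1.3.2.1 joins the two limits with *and*.

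**Working it through.** **1. The protocol's own margins (Section 1.3.2.1).** Against convulsive exposures in dogs: 8230/1560 = 5.28 and 14600/2490 = 5.86. Against exposures with behavioural signs: 4490/1560 = 2.88 and 7850/2490 = 3.15. The stated margins of about 5-, 6- and 3-fold are reproduced.

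**2. The two rules side by side.**

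| State | Escalation condition (A or B) | Stopping rule (not A, or not B) |
|---|---|---|
| A and B | met | no stop |
| A only | met | stops the planned next dose; lower interim doses possible |
| B only | met | stops |
| Neither | not met | stops |

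The condition is met in three states; the stopping rule permits the planned next dose in one. The B-only state matters most, because there the predicted mean is above the cap.

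**3. A bound with no variability assumption.** If B holds, every observed value is at or below the limit L, so the current geometric mean is too. A dose-proportional prediction for a step of factor f is then at most f × L. The 5 to 10 mg and 10 to 20 mg steps have f = 2:

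- AUC0-24h: 2 × 2490 = 4980 nM*h, and 4980/7850 = 63% of the dog exposure with behavioural signs.
- Cmax: 2 × 1560 = 3120 nM, and 3120/4490 = 69%.

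These are ceilings on what the wording tolerates, not expected exposures.

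**4. The protocol's own prediction.** Section 1.2.5 gives AUC0-inf 330 nM*h and Cmax 52 nM at 2 mg, that is 165 nM*h and 26 nM per mg. AUC0-inf stands in for AUC0-24h; with an effective half-life of 2.7 h about 0.2% lies beyond 24 h (2^(−24/2.7) ≈ 0.002). Assuming linear scaling:

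- 10 mg: 1650 nM*h; 1650/2490 = 66% of the limit.
- 20 mg: 3300 nM*h; 3300/2490 = 133% of the limit.
- 20 mg Cmax: 520 nM; 520/1560 = 33% of the limit.
- The caps are reached at 2490/165 = 15.1 mg (AUC) and 1560/26 = 60 mg (Cmax), so AUC is the limit that binds.

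At the 10 to 20 mg step A fails on AUC, and the outcome turns on B.

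**5. Chance that B still holds at that step.** The documents give no between-subject variability, so geometric CVs of 20, 30 and 40% are assumed. With lognormal values, σ = √ln(1 + gCV²) and P(no one of n over the limit) = Φ(ln(2490/1650)/σ)^n. The sizes are n = 6 actives per group, and n = 3 because Section 3.1 accepts "Preliminary pharmacokinetic data of at least 3 subjects on active treatment for up to at least 24 h post dosing".

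| Assumed gCV | n = 6 | n = 3 |
|---|---|---|
| 20% | 89.2% | 94.4% |
| 30% | 60.4% | 77.7% |
| 40% | 39.7% | 63.0% |

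Holding the observed geometric mean of six subjects at exactly 1650 nM*h (simulation, 1,000,000 draws) gives 93.2, 64.9 and 38.6%. These figures say how often the condition would be met with the cap predicted to be exceeded. They do not say how often anyone would be dosed, since the stopping rule still fires.

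**The case against.** The strongest reply is that no dosing decision changes. The escalation bullet is only a necessary condition, so meeting it authorises nothing. The stopping rule is unconditional, Section 3.1 requires that no stopping criterion has been met, and Sections 1.3.2.1 and 1.3.2.2 repeat the cap. Section 1.4 also directs the reader correctly to Section 1.4.7 for "measures of risk minimization (including safety precautions and stopping rules". This stands: both rules can be obeyed, the stricter governs, and a careful team would follow it. It limits the consequence but does not make the condition right.

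Second, the operative text may have changed. Section 11.7 says Amendment 7 adapted the rules in Section 1.4.7 to new exposure limits and added human data from dose groups 1 to 6, that is up to 20 mg. The amended rule text and the observed exposures are not shown, so the visible limits appear to have governed steps already taken. This also stands. The finding is confined to the visible text, and the numerical example is an illustration of it.

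Third, A alone has a legitimate use, because the stopping rule allows lower interim doses judged on the expected geometric mean. This is correct, and a bare swap of *or* for *and* could seem to bar those doses. The fix must keep them.

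Fourth, the Cmax ceiling of 3120 nM is far above the 520 nM predicted at 20 mg, and the 5 to 10 mg step would not approach the AUC ceiling. Both are true; the realistic case is AUC at 10 to 20 mg. The loose wording within A would also ordinarily be read as meaning that neither value exceeds its limit. That reading does not help with the outer *or*, which opens a second complete condition.

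**Conclusion.** The concern holds for the visible text and should be fixed. Section 1.4.7 contains an escalation condition that is more permissive than its own stopping rule in two of four states, and in one of them it does not enforce the geometric mean cap. Under linear scaling of the protocol's prediction, that state can arise at the 10 to 20 mg step, with predicted AUC at 133% of the limit. How often the condition would still be met (40 to 89% on six subjects) depends entirely on the assumed CV. The defect is a go or no-go rule that is too loose as written, not evidence of an unsafe escalation. The wrong cross-reference in Section 3.1 is certain and needs no assumption.

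**What to change.** In the escalation bullet of Section 1.4.7, state that the planned next higher dose is given only if neither the predicted geometric mean Cmax nor the predicted geometric mean AUC0-24h exceeds its limit, **and** no individual value in the current dose group exceeds either limit. Add that if this is not met, the dose-group stopping rule of Section 1.4.7 applies, including its allowance for one or two lower interim doses judged on expected geometric mean exposure. In Section 3.1, change both references to Section 3.3.4.2 to Section 1.4.7. If the Amendment 7 text uses the same connective, make the same change there.

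The cost is a protocol amendment for wording and two cross-references. No subjects, samples or procedures are added.

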#### Stopping Rules Related to Individual Subjects:

- Occurrence of one adverse event of severe intensity (including but not limited to QT prolongation, dissociative symptoms or a decrease in vigilance) assessed as related to the study drug by the investigator
- Occurrence of one serious adverse event assessed as related to the study drug by the investigator

[figure not shown]
#### Stopping Rules Related to Dose Groups:

- In case of any safety concerns, as listed below but not limited to them, the trial will be mandatorily discontinued. Occurrence of severe non-serious adverse events

considered as drug-related by the investigator in 2 subjects of the same dose group (8 subjects) in the SRD-Part, or 3 subjects of the BA/ FE group (12 subjects), or occurrence of at least one drug-related serious adverse event (SAE). Moreover, dose escalation in the SRD-Part will be terminated, if more than 3 of the actively dosed subjects at one dose level show drug-related and clinically relevant adverse events of at least moderate intensity.

- Clinical apparent seizures/ convulsions in one or more subjects in the same dose group.
- EEG changes consistent with pro-convulsive activities (e.g., spike and wave) that is considered to be drug-related in two or more subjects of the same dose group.
- Clinically relevant changes in the neurological assessment indicating dose-limiting intolerance that is considered to be drug-related in one or more subjects of the same dose group.
- Dose escalation in the SRD-Part or treatment in the BA/ FE-Part will be stopped, if at least 2 subjects on active treatment at one dose level (SRD-Part) or 2 subjects in the BA/ FE-Part have relevant individual QT prolongations, i.e., a QTc increase of greater than 60 ms from baseline and/ or an absolute QT or QTc greater than 500 ms, as confirmed by a repeat ECG recording.
- Dose escalation in the SRD-Part will be stopped, if the  $C_{\max}$  or  $AUC_{0-24h}$  of at least 1 subject of one dose group increases above the following exposure thresholds or if the estimated geometric mean exposure is expected to exceed a  $C_{\max}$  of 1560 nM or an  $AUC_{0-24h}$  of 2490 nM\*h. In this case, one or two additional dose levels lower than the planned next dose level may be given, as long as the expected geometric mean exposure values of the interim dose do not exceed these exposure thresholds. Estimation will be done based on preliminary pharmacokinetic results of preceding dose groups (see Section [7.4](#))

**Applicable for Amendment No. 7**

#### 1.4.8 Overall assessment and conclusion

Based on the well-characterized mode of action, nature of target, high relevance of used animal models and the comprehensive non-clinical safety package of BI 1569912, and taking into account specific safety measures, a participation in this single dose regimen does not represent an undue risk to healthy subjects. Considering the medical need for a better MDD treatment and taking into account the potential advantage of a highly selective NR2B negative allosteric modulator, the expected benefit of this trial is likely to outweigh the potential risks and justifies the exposure of healthy subjects to BI 1569912.

## 2. TRIAL OBJECTIVES AND ENDPOINTS

### 2.1 MAIN OBJECTIVES, PRIMARY AND SECONDARY ENDPOINTS

#### 2.1.1 Main objectives

Main objectives of this trial are to investigate for

SRD-Part: Safety, tolerability, pharmacokinetics and pharmacodynamics following single rising doses of BI 1569912

BA/FE-Part: (a) the relative bioavailability of BI 1569912 PfoS and tablet, and  
(b) the influence of food on the relative bioavailability of the BI 1569912 tablet

#### 2.1.2 Primary endpoint

SRD-Part: The primary endpoint for assessment of safety and tolerability of BI 1569912 is the percentage of subjects with drug-related adverse events.

BA/FE-Part: The following pharmacokinetic parameters will be determined for BI 1569912:

- $AUC_{0-tz}$  (area under the concentration-time curve of the analyte in plasma over the time interval from 0 to the last quantifiable data point)
- $C_{max}$  (maximum measured concentration of the analyte in plasma)

[figure not shown]
#### 2.1.3 Secondary endpoint

[figure not shown]
SRD-Part: The following pharmacokinetic parameters will be determined, if feasible:

- $AUC_{0-\infty}$  (area under the concentration-time curve of the analyte in plasma over the time interval from 0 extrapolated to infinity)
- $C_{max}$  (maximum measured concentration of the analyte in plasma)

BA/FE-Part: The following pharmacokinetic parameter will be determined for BI 1569912:

[figure not shown]
- $AUC_{0-\infty}$  (area under the concentration-time curve of the analyte in plasma over the time interval from 0 extrapolated to infinity)

[figure not shown]

#### 2.2.2.2 Further BI 1569912 specific endpoints of safety and tolerability

- Columbia-Suicide Severity Rating Scale (C-SSRS)
- Standardized physical/ neurological assessment
- Assessment of dissociative symptoms (e.g., CADSS)
- Electroencephalogram (EEG)

### 3. DESCRIPTION OF DESIGN AND TRIAL POPULATION

#### 3.1 OVERALL TRIAL DESIGN AND PLAN

[figure not shown]

Figure 3.1: 1 Overall study design

#### SRD-Part

This single-rising dose part will be performed as a single-blind, partially randomised within dose group, placebo-controlled parallel-group trial.

It is planned to include a total of 72 healthy male subjects in the trial. The subjects will be assigned to 9 groups consisting of 8 subjects per group. These groups will be dosed sequentially (see Table [3.1: 1](#)). The investigator (after consultation with the sponsor) is allowed to alter the scheduled dose groups (e.g., add low and/or intermediate dose groups) on

the basis of experience gained during the study (for instance, based on preliminary pharmacokinetic data), under the condition that the planned and approved highest dose is not exceeded. Thus, the actual number of subjects entered may be more than 72 but is not to exceed 88. Such changes may be implemented via non-substantial CTP amendments.

However, the addition of further dose groups exceeding the already tested dose levels for the evaluation of safety findings will be subject to a substantial CTP amendment requiring approval.

Within each dose group, 6 subjects will receive BI 1569912 and 2 will receive placebo. Only one dose is tested within each dose group.

In the SRD-Part, for safety reasons, each dose group of 8 subjects (6 on active, 2 on placebo) will be divided into three cohorts (for details, see Section [1.4.7](#), 'General Risk Minimization Measures').

The dose groups to be evaluated are outlined in Table [3.1: 1](#) below.

Table 3.1: 1                      Dose groups

| Dose Group                    | 1    | 2    | 3 | 4 | 5  | 6  | 7  | 8  | 9  |
|-------------------------------|------|------|---|---|----|----|----|----|----|
| Daily dose (mg)               | 0.25 | 0.75 | 2 | 5 | 10 | 20 | 30 | 40 | 50 |
| Number of subjects            | 8    | 8    | 8 | 8 | 8  | 8  | 8  | 8  | 8  |
| Subjects receiving placebo    | 2    | 2    | 2 | 2 | 2  | 2  | 2  | 2  | 2  |
| Subjects receiving BI 1569912 | 6    | 6    | 6 | 6 | 6  | 6  | 6  | 6  | 6  |

The groups will be dosed consecutively in ascending order, and a time interval of at least 7 days will be maintained between the last drug administration to subjects in the previous dose group and the first drug administration to subjects in the subsequent dose group. The decision to treat the next dose group will be based upon safety, tolerability and pharmacokinetic data of all the preceding dose groups. The next dose group will only be applied, if, in the opinion of the Principal Investigator (or an authorised deputy) and the Clinical Trial Leader (or an authorised deputy), no safety concerns have arisen in the preceding dose groups (i.e., no dose-limiting events occurred) and, if none of the pre-specified trial-specific stopping criteria have been met (refer to Section [3.3.4.2](#)).

A documented safety review must take place prior to each dose escalation. Furthermore, an unscheduled safety review meeting can be requested anytime by the Principal Investigator (or an authorised deputy) or the sponsor of the study (for instance, due to the occurrence of any unforeseen adverse events).

Although no formal safety review meeting will take place within a given dose group, safety will be continuously monitored during this trial, and an individual will only be dosed in the absence of any safety concern (i.e., no dose-limiting events occurred) and if none of the pre-specified trial-specific stopping criteria have been met (refer to Section [3.3.4.2](#)).

At a minimum, the following data need to be available for review to escalate to a higher dose.

- AEs in the current and preceding dose groups up to at least 48 h post dosing, including clinically relevant findings from ancillary safety testing listed below (Note: AEs may be ongoing at the time of Safety Reviews and AE information may be subject to change prior to Database Lock)
- Results from 12-lead ECG and continuous ECG monitoring in the current and preceding dose groups up to at least 48 h post dosing
- Vital signs in the current and preceding dose groups up to at least 48 h post dosing
- Clinical laboratory tests in the current and preceding dose groups up to at least 24 h post dosing
- EEG reports up to at least 24 h post dosing
- Preliminary pharmacokinetic data of at least 3 subjects on active treatment for up to at least 24 h post dosing as per Section [7.4](#)
- Check of criteria for stopping subject treatment as per Section [3.3.4.1](#)

The decision to escalate the dose will be made jointly by the Principal Investigator (or an authorised deputy) and the Clinical Trial Leader (or an authorised deputy) after in-depth analysis of all available safety data, especially SAEs (if occurred), AEs, and out-of-range laboratory results (if considered clinically relevant). In addition and depending on the results and findings, suitable experts from the sponsor or external institutions (e.g., [REDACTED]) may be consulted on an 'as needed' basis. In these cases, expert recommendations will be documented in the minutes of the safety review and considered for the decision making. Dose escalation will only be permitted, if no safety concerns exist neither in the opinion of the Principal Investigator (or an authorised deputy) nor the Clinical Trial Leader (or an authorised deputy).

Safety Reviews can be conducted face-to-face or by video/telephone conference. The Clinical Trial Leader is responsible for the organisation and minutes of the reviews. Minutes will be signed off by the Principal Investigator (or an authorised deputy) and Clinical Trial Leader (or an authorised deputy), and will be filed in the ISF and TMF.

An overview of all relevant trial activities is provided in the [Flow Chart](#). For visit schedules and details of trial procedures at selected visits, refer to Sections [6.1](#) and [6.2](#), respectively.

